4.0 Study Endpoints – Overall we will test whether thalamic LIFUP during a pain provocation is safe and feasible. In addition, we will test the following endpoints.

4.1. Primary endpoint: Thalamic LIFUP will modulate pain ratings measured by administering cutaneous hot and cold stimuli via the Medoc Pathway System.

4.2. Secondary endpoints: Thalamic LIFUP will reduce BOLD activity in the thalamus.

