10.0 Study Design/Methods

10.1. Study Design. Twenty healthy volunteers between 18-65 years of age without history of depression or chronic pain will be recruited to participate in this sham-controlled, double-blind crossover study, all within one session within the MRI scanner. All participants will receive 10 minutes of sham LIFUP, 20 minutes of rest, and 10 minutes of real LIFUP within the MRI scanner using the BXPulsar 1001, Brainsonix Inc. The order will be counterbalanced. The duration of the LIFUP analgesia and BOLD effects will be determined.

10.2. Behavioral Measures. We will begin baseline pain assessments by administering cutaneous hot and cold stimuli via the Medoc Pathway System (Medoc, Durham, NC) using a 30 x 30 mm ATS thermode. There will be two behavioral measures: quantitative sensory testing (QST) on untreated skin and blocks of pain on capsaicin-treated skin.

QST will be done using method of limits testing on the thenar eminence of the right hand. A program will be set up to administer 10 hot stimuli with random durations between each trial. The ATS thermode begins at 32°C and increases by 0.5°C per second. Participants will be asked to press a button in order to signify three different measures: (1) sensory threshold, or the temperature at which the stimulus becomes noticeable, (2) pain threshold, or the temperature at which the stimulus becomes painful, and (3) pain tolerance, or the temperature at which the stimulus becomes too painful to tolerate. Measuring these thresholds will yield information about

A β , A δ , and C fibers, respectively. The device will be set to stop heating at 51.5° C and stop cooling at 0° C to avoid tissue damage. These ten trials will be performed once before and once after each scanning block, either with thalamic LIFUP or 'fake' thalamic LIFUP.

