12.0 Data Management

The behavioral pain measures will be examined using a repeated measures ANOVA with time and condition (LIFUP, sham) as between group variables. These will be paired data within each subject.

Justification of Sample Size: Prior studies by our group using this same paradigm have shown differences in pain intensity with prefrontal TMS, or blocking of opiates. (29)

Consent procedures will be carried out within a private room inside the IOP. Data acquisition will be performed within the MUSC CBI research scanner at [name] The data will not be labeled with identifiable information. Participants will be identified on all research records solely by a number, ensuring confidentiality of all data. Any information that is obtained in connection with this study and that could identify the participants will remain confidential and will not be released or disclosed without their further consent, except as specifically required by law. If the results of this research are presented at scientific meetings, participant identity will not be

disclosed. All conversations with participants will take place behind closed doors in front of only the participant and designated caregivers, family, or friends.

Any imaging or other research data will be stored in a de-identified manner.

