12.1. fMRI Data Analysis: Individual fMRI Data Analysis (first level analysis): The fMRI data will be analyzed blind to LIFUP activation. MR scans will be transferred into ANALYZE format with MRICro (<http://www.sph.sc.edu/comd/orden/mircro.html>) and then further processed in Matlab 7.3 (Mathworks, Sherborn, MA) with Statistical Parametric Mapping software 12 (SPM12, The Wellcome Department of Cognitive Neurology, London, <http://www.fil.ion.bphf.ac.uk>). Default settings were used unless indicated otherwise. All volumes will be realigned to the first volume. After realignment, for all subjects, movement across the 8 minutes scan must be less than 0.5 mm in 3 axes and less than 0.5 degree in 3 orientations. The images will be normalized stereotactically into a standard space with a resolution of 3 mm³ voxels using the averaged functional EPI image – the Montreal Neurological Institute (MNI) EPI template in SPM12. Subsequently, the data will be smoothed with an anisotropic 8 mm³ Gaussian kernel and high-pass filtered (cut-off period=128s). In a first level of statistical analysis, using a boxcar function convolved with the modeled hemodynamic response function as the basic function for the general linear model, we will obtain contrast-maps of the difference between task and rest for each subject. The six head movement parameters will be included as confounds.

Group Data Analysis (the second level analysis): Subject-specific contrasts will be entered into a second-level analysis to obtain a random effect analysis of activation effects across the entire group. The combined group *t* maps will be thresholded at $p \leq 0.05$ corrected for multiple comparisons (family-wise error, FWE) and cluster analyses will be performed with a spatial extent threshold of 5 voxels.

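### Section 12.0 sets no deciding outcome, ANOVA term, alpha or multiplicity rule for the behavioural pain measures, so any of several tests could carry the claim that LIFUP modulates pain

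*Combined protocol and SAP*

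**What the plan says.** The behavioural analysis in section 12.0 is two sentences: "The behavioral pain measures will be examined using a repeated measures ANOVA with time and condition (LIFUP, sham"), both factors being described as between-group, then "These will be paired data within each subject".

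The outcomes that feed it are defined in section 10:

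- Section 10.2: "There will be two behavioral measures: quantitative sensory testing (QST) on untreated skin and blocks of pain on capsaicin-treated skin".
- For QST: "Participants will be asked to press a button in order to signify three different measures". These are sensory threshold, pain threshold and pain tolerance, each recorded as a temperature. On timing: "These ten trials will be performed once before and once after each scanning block".
- For the capsaicin-treated skin, a 1-10 intensity rating follows each heat trial. There are 12 trials at a single baseline scan, 12 after sham and 12 after real LIFUP.
- Section 10.3 adds a pain-intensity rating at the end of each functional scan.

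The effect of interest changes with the section. The primary endpoint in 4.1 is: "Thalamic LIFUP will modulate pain ratings measured by administering cutaneous hot and cold stimuli via the Medoc Pathway System". The hypothesis in section 1.0 is an increase in pain tolerance. The description of device use in section 3.0 speaks of changes in pain threshold.

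Section 12.1 thresholds the group imaging maps at 0.05 "corrected for multiple comparisons (family-wise error, FWE"). Nothing comparable is stated for the behavioural tests: no alpha, hierarchy, named contrast or exploratory label.

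**The concern.** Two choices are left open at once: which outcome decides, and which ANOVA term. QST is measured before and after each block, so both the condition term and the time-by-condition term can be estimated, and either could be presented as the LIFUP effect. Several correlated tests could then each support the main behavioural claim, with no limit on the overall false-positive rate.

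The outcomes can also disagree. If tolerance rises while the rating of the fixed 7-out-of-10 heat stimulus does not change, the plan cannot say whether the study was positive. This is more than silence on a detail, because three sections point to three different outcomes. The study is described as a proof of concept, and section 1.0 expects later studies in other conditions to follow, so an ambiguous positive result would carry weight.

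**Working it through.** **No figure to reproduce.** The documents give no behavioural alpha, power, effect size or family-wise error rate.

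**Inputs from the documents.** Three QST outcomes and one capsaicin-heat rating (10.2); a possible fifth outcome (10.3); QST before and after each block; one shared baseline for the rating; paired data (12.0); N = 20 (10.1) or 35 (6.0).

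**Assumptions.** Two-sided 0.05 per test; no true effect; a paired analysis; equal correlation r between outcomes, varied from 0 to 0.9; condition and time-by-condition contrasts of one outcome independent of each other.

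**Number of tests.** One term each gives 4. Both terms for the three QST outcomes and one for the rating gives 3 × 2 + 1 = 7; this fits the shared baseline, which leaves the rating without a pre-value per condition. Both terms for all four gives 4 × 2 = 8.

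**Independent tests.** Chance of at least one false rejection = 1 − 0.95^k:

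- k = 1: 5.0%
- k = 2: 9.75%
- k = 4: 1 − 0.8145 = 18.5%
- k = 5 (end-of-scan rating added): 22.6%
- k = 7: 30.2%
- k = 8: 33.7%

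**Correlated outcomes.** Simulation of paired t-tests at N = 20, with 20,000 simulated trials per setting; the r = 0 row is the exact result above:

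| r between outcomes | 4 tests | 7 tests | 8 tests |
|---|---|---|---|
| 0 | 18.5% | 30.2% | 33.7% |
| 0.3 | 17.6% | 28.8% | 32.0% |
| 0.5 | 15.8% | 26.6% | 29.1% |
| 0.7 | 13.1% | 22.4% | 24.3% |
| 0.9 | 9.5% | 17.1% | 18.1% |

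Sample size hardly matters. At N = 35 and r = 0.5 the three figures are 16.0%, 26.9% and 29.4%; at r = 0.9 they are 9.4%, 17.2% and 18.1%. The ranges are therefore about 9-19% for one term and about 17-34% for both.

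**Narrow reading of 4.1.** If only the capsaicin-heat rating is primary, the risk is 5% with one term and 1 − 0.95² = 9.75% with two, provided that time is given a meaning for that outcome.

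**Literal between-group fit.** Fitting condition as a between-group factor to paired data (N = 20, correlation 0.4 between outcomes, four outcomes, one term, 5,000 simulated trials) gives 16.7%, 7.7%, 3.1% and 0.3% at within-subject correlation 0, 0.3, 0.5 and 0.7.

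**After the fix.** One outcome and one contrast at 0.05 gives 5%. For comparison, Bonferroni over four independent tests gives 1 − (1 − 0.0125)^4 = 4.9%.

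**The case against.** The strongest reply is that 4.1 already chooses. It names pain ratings, section 10.2 uses that term for the capsaicin-heat blocks, and the QST outcomes are temperatures at a button press, not ratings. This reading is plausible, and it is why 5% belongs among the results. It is not secure. The rest of the 4.1 sentence, on hot and cold Medoc stimuli, closely matches the opening of 10.2, which introduces both measures. The blocks themselves use heat only. The hypothesis and section 3.0 point to tolerance and threshold. Even if the reading is accepted, the deciding term stays open.

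A reader might infer one flat false-positive rate, say 16% for one term, or 29% as a ceiling for two. The documents support neither. Both figures need an alpha of 0.05 and a correlation near 0.5, which are not stated, and independence gives more than 29%.

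A reader might also take these rates to describe the model exactly as written. They do not: 12.0 calls the factors between-group, and that fit to paired data becomes conservative as within-subject correlation rises. The paired reading is an interpretation, though a reasonable one, since the next sentence of 12.0 says the data are paired. Correcting the model to match the crossover brings the multiplicity back.

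Nor are these the rates of a false claim of analgesia. They count rejections in both directions, which matches the verb in 4.1. For the analgesic direction alone, four independent tests give 1 − 0.975^4 = 9.6%.

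Finally, sensory threshold is not a pain measure. Without it, three independent tests give 1 − 0.95³ = 14.3%, still above 5%.

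**Conclusion.** The gap is real: no outcome, term, alpha or multiplicity rule settles the behavioural claim, and the sections conflict on the effect of interest. The size of the inflation is conditional. At an assumed two-sided 0.05 per test and a paired analysis, the risk of at least one false claim of modulation is about 9-19% over four outcomes, or about 17-34% if both LIFUP-related terms count. It falls to 5%, or about 10% with two terms, if 4.1 means the capsaicin-heat rating alone. The correlation between outcomes is unknown, so no single value in these ranges can be presented as the plan's error rate. That the deciding test is unidentified does not depend on any of these assumptions.

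**What to change.** In 4.1 and 12.0, name one primary outcome and one deciding contrast: within-subject real minus sham, at two-sided 0.05. Each participant's mean capsaicin-heat block rating is one candidate. Pain tolerance is another if the sponsor prefers it, in which case the text should say whether the post-block value or the pre-to-post change is compared. Align the hypothesis and section 3.0 with the choice, and describe condition and time as within-subject factors.

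Label the remaining QST outcomes, the end-of-scan rating and any other non-primary rating as secondary or exploratory, reported with confidence intervals. If any of them is to support a significance claim, apply Holm's correction across those that do; testing them only after the primary succeeds is optional. Keep time-by-condition as a named secondary analysis, because Aim 2 asks for the time course of analgesia. If change in tolerance is chosen as primary, say that its deciding contrast is this same term.

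The cost is protocol wording, with no new data or participants. The downside is that a significant result on a non-primary outcome alone could no longer be reported as a positive study.

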When I first proposed to do TMS in the scanner over 20 years ago the MUSC IRB required that I be the first test subject, and report back. I did that and am prepared to do that here if that is what is needed. I think this LIFUP is as safe as diagnostic ultrasound, and has enormous research and clinical potential.)

Specific Aims.

- Aim 1.** Test the safety and feasibility of LIFUP to thalamus in healthy volunteers.
- Aim 2.** Characterize the time course and magnitude of thalamic LIFUP-induced analgesia.
- Aim 3.** Identify the brain circuitry (BOLD activity) that thalamic LIFUP changes during induced pain.

Hypothesis.

The anterior nuclei of the thalamus in addition to periaqueductal gray (PAG) and rostral ventromedial medulla (RVM) are integral regions of a supraspinal opioidergic structure that regulate pain perception (4-8). With the capability to influence deep neurological tissues, low intensity frequency ultrasound pulsation can likely modulate this circuit and induce analgesia. LIFUP deep brain modulation is achieved by induction of focused mechanical waveforms that traverse the cranium and underlying brain tissue (19). The low frequency of the ultrasonic wave consequently alters neuronal transmission and causes action potential variations through mechanical means, rather than thermal (20). The purpose of this study is to examine whether stimulation of the anterior nuclei of the thalamus via LIFUP induces analgesia. **We hypothesize that suppression of the anterior nuclei of the thalamus will induce a temporary increase**

in pain tolerance. Moreover, the behavioral changes in pain will correlate with specific regional BOLD changes during pain.

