10.3. Magnetic Resonance Imaging (MRI). A Siemens 3T Trio MRI scanner will be used for imaging. After QST testing, the MR compatible ATS thermode will be placed on the capsaicin-treated right volar forearm. Participants will undergo standard high-resolution anatomical scans prior to undergoing functional scans during which 22 second blocks of heat will alternate with 22 second blocks of rest. These heat stimuli were previously rated as "7 out of 10" in intensity during baseline testing. Each fMRI scan will involve 12 pain/rest blocks. At the end of the functional scan, each participant will rate the intensity of the pain that they experienced. The functional pain/rest scan will be repeated three separate times throughout the experiment: (1) at baseline, (2) after 20 min of sham LIFUP, and (3) after 20 min of real LIFUP. A short interleaved LIFUP-fMRI scan will be performed immediately before the pain/rest block scans after sham LIFUP and real LIFUP. During these sessions, the LIFUP machine will fire single pulses at 1Hz frequency. A TR delay will be used to minimize LIFUP-induced destruction of acquired scan data. E-Prime software will be used to trigger LIFUP pulses and coordinate them with scanner TR delays. The purpose of the interleaved LIFUP-fMRI sequence is to examine how LIFUP affects BOLD signal changes in real time.

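### The fMRI analysis in section 12.1 maps pain activation only: with no LIFUP-versus-sham BOLD contrast and no thalamic region, it does not test endpoint 4.2 or Aim 3

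*Combined protocol and SAP*

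**What the plan says.** The imaging objectives are about an effect of LIFUP. The secondary endpoint (section 4.2) is "Thalamic LIFUP will reduce BOLD activity in the thalamus". Aim 3 (section 1.0) is to "Identify the brain circuitry (BOLD activity) that thalamic LIFUP changes during induced pain". The Hypothesis in section 1.0 adds that "the behavioral changes in pain will correlate with specific regional BOLD changes during pain".

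Section 10.3 plans three pain/rest scans per subject: "1) at baseline, (2) after 20 min of sham LIFUP, and (3) after 20 min of real LIFUP". It also plans a short interleaved scan after each sonication condition: "The purpose of the interleaved LIFUP-fMRI sequence is to examine how LIFUP affects BOLD signal changes in real time".

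Section 12.1 gives the analysis. The first level yields "contrast-maps of the difference between task and rest for each subject". The second level reads: "Subject-specific contrasts will be entered into a second-level analysis to obtain a random effect analysis of activation effects across the entire group". Group t maps are thresholded at FWE-corrected p ≤ 0.05 with a 5-voxel extent. LIFUP appears in 12.1 only where the analyst is to be blinded to it.

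The one analysis with a condition factor is in section 12.0: "The behavioral pain measures will be examined using a repeated measures ANOVA with time and condition (LIFUP, sham) as between group variables". It covers behavioural measures only.

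**The concern.** A group map of heat minus rest shows where the brain responds to heat pain. It does not show whether that response is lower after LIFUP than after sham, which is what 4.2 asserts and Aim 3 explores. The planned result could look the same whether or not LIFUP does anything.

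Several choices are left open until after the data are seen: comparator (sham or baseline), scan (pain/rest or interleaved), region (whole thalamus as in 4.2, or the anterior nuclei named in the Hypothesis), search volume for the FWE correction, and whether the three scans are pooled or mapped separately. 4.2 is the only secondary endpoint and Aim 3 is one of three aims, so the whole imaging part of the trial depends on these choices.

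**Working it through.** **1. Objective against analysis.** There is no planned figure to reproduce, because the documents give no effect size, SD or power for BOLD.

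| Objective | What it needs | What 12.0 and 12.1 give |
|---|---|---|
| 4.2: lower thalamic BOLD | Condition contrast, thalamic region | Heat minus rest, no region |
| Aim 3: circuitry changed by LIFUP | Condition contrast, whole brain | Heat minus rest, combined group map |
| Hypothesis: pain change tracks BOLD change | Correlation of two within-subject differences | Nothing |
| 10.3: interleaved scan | First-level model for single pulses at 1 Hz | Nothing |

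The boxcar model in 12.1 fits the pain/rest scan: 12 × (22 + 22) s = 528 s = 8.8 min, close to the 8 minutes mentioned there. It does not describe the interleaved scan.

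**2. Contrast weights.** Over the scans (baseline, sham, LIFUP), pooled activation has weights (1/3, 1/3, 1/3) and the LIFUP effect has (0, −1, +1). Their product is 0 − 1/3 + 1/3 = 0. The contrasts are orthogonal, so the pooled map does not estimate the LIFUP effect.

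**3. If the scans are pooled (illustration).** Assumptions: thalamic-mean heat-minus-rest value with SD 1 in each scan, between-scan correlation ρ of 0.3 to 0.7, mean activation d of 1.0 to 1.5, one two-sided test at 0.05. Let dz be the mean LIFUP-minus-sham difference divided by its SD; LIFUP then lowers its scan by dz × √(2(1−ρ)).

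Worked case with N=20, ρ=0.5, d=1.0:
- SD of the three-scan mean = √((1 + 2×0.5)/3) = 0.816.
- No LIFUP effect: noncentrality = (1/0.816) × √20 = 5.48, so power exceeds 99.9%.
- dz=1.0: the LIFUP scan falls by 1.0 × √(2×0.5) = 1 SD and the pooled mean to 1 − 1/3 = 0.667. Noncentrality = (0.667/0.816) × √20 = 3.65, so power is about 93%.

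Simulation over the full range (20,000 trials per setting):

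| | No LIFUP effect | dz = 1.0 |
|---|---|---|
| Pooled test, N=20 | 99.7-100% | 93-100% |
| Pooled test, N=35 | 100% | 99.6-100% |
| Direct test, N=20 | about 5% | 99% |

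**4. If separate maps are compared (illustration).** Same set-up, no LIFUP effect, d from 0.2 to 1.0. The pattern in which sham is significant and LIFUP is not peaks at about 13-21% of trials at N=20 or 35, depending on ρ. A direct two-sided test at 0.05 would falsely show a reduction in 2.5%. The peak occurs where each map has roughly 40-60% power; at d=1.0 the figure is about 1% or less.

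**5. The direct test.** Noncentral t, two-sided 0.05, df = N − 2 (one order term), noncentrality = dz × √N:

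| | N=20 (section 10.1) | N=35 (section 6.0) |
|---|---|---|
| dz for 80% power | 0.66 | 0.49 |
| Power at dz = 0.5 | 56% | 82% |

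These assume that the mask mean shows the stated dz. A focal effect would be diluted over a larger mask.

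**The case against.** The strongest reply is that the text is incomplete, not wrong. In a crossover with one cohort, a group analysis can simply mean all subjects, and blinding the analyst to LIFUP makes sense only if scans are distinguished by condition. The team may well intend a condition contrast. But none is written anywhere, and the only contrast defined is heat minus rest. Separate maps by condition, if that is the intention, would still not test their difference.

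Several narrower objections stand:
- The missing thalamic region bears only on 4.2. Aim 3 needs the condition contrast, not a region. Even for 4.2, a whole-brain condition contrast would cover the thalamus; a mask makes the test specific and gains power.
- Sham can be inferred as the comparator from the sham-controlled design, though 4.2 does not say so.
- The simulations use one region without correction, so they are not error rates of the FWE maps in 12.1. The pooled figures assume strong pain activation and the separate-map peak assumes weak activation, so the two must not be added together.
- An order term is good practice in a counterbalanced crossover but is not essential to validity here. It costs one degree of freedom, about 0.2 percentage points of power at dz=0.5 with N=20.

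None of these supplies the missing comparison.

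**Conclusion.** The concern holds, and the section should be corrected before the imaging data are analysed. Followed exactly, 12.1 cannot confirm or refute endpoint 4.2 or Aim 3. This rests on the text alone and needs no assumed effect size. The percentages only illustrate it, under assumed activation, correlation and a single uncorrected region: the pooled test is almost always significant with or without a LIFUP effect, and comparing separate maps can suggest a reduction up to about eight times as often as a direct test would (21/2.5 = 8.4, worst case).

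The two sample sizes, 20 in section 10.1 and 35 in section 6.0, must be reconciled. They change the power of the corrected test but not this conclusion. The primary pain endpoint is not affected.

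**What to change.** Rewrite the second level of section 12.1:

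1. For each subject form (heat minus rest after LIFUP) − (heat minus rest after sham). Test it with a within-subject random-effects model: paired or one-sample t, or flexible factorial. If a sequence term is included, mean-centre it. With 0/1 coding the intercept estimates the LIFUP effect in one order only; with 10 of 20 subjects per order its SE rises by √2 = 1.41, and power at dz=0.5 falls from 56% to 32% (N=35, orders of 17 and 18: from 82% to 52-54%).
2. For endpoint 4.2, name sham as the comparator and say which scan is used. If it is the interleaved scan, add its first-level model. Test the mean contrast in a pre-specified anatomical mask at two-sided 0.05, with small-volume FWE correction for localisation. State whether the mask is the whole thalamus or the anterior nuclei.
3. For Aim 3, report the whole-brain FWE-corrected map of the same contrast and name the search volume.
4. For the Hypothesis in section 1.0, correlate the LIFUP-minus-sham difference in pain rating with the BOLD difference, in regions named in advance.
5. State the role of the baseline scan.

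The cost is analysis wording and a little more analysis work. The post-sham and post-LIFUP scans are already planned for every subject, so no new data are needed.
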